9.9 Treatment Compliance

This study involves a single sub-retinal injection of a volume of up to 0.1 mL AAV2-REP1 in each eye. Measure of treatment compliance with AAV2-REP1 is therefore not necessary.

Compliance with the use of prednisone/prednisolone will be captured in the eCRF; subject diary cards will be provided to participants prior to each surgery.

10 STUDY VISITS AND PROCEDURES

The schedule of study procedures is presented in [Table 1](#).

At each study visit, an attempt should be made to perform all procedures in both eyes.

10.1 Screening Period

The Investigator will explain the study purpose, procedures and subject responsibilities to each potential study subject. The subject's willingness and ability to meet the protocol requirements will be determined.

Prior to any study-specific procedure, written informed consent will be obtained. The subject will sign and date 1 copy of the consent form in the presence of the Investigator or his/her designee. The original signed form will be retained at the study site and an additional copy will remain in the subject's medical records; a copy will also be given to the subject.

After informed consent has been obtained, the subject will be allocated a subject identifier and evaluated to determine study eligibility.

Screening procedures will consist of the following (all ophthalmic assessments will be conducted on both eyes):

- Demography, medical and ocular history
- Vital signs
- Weight
- Vector shedding sampling – blood, tears (both eyes), urine, saliva
- Immunogenicity sampling
- BCVA
- Microperimetry
- Full ophthalmic examination, including IOP, a slit-lamp examination, lens opacity, and dilated fundus examination
- SD-OCT
- AF
- 7-field colour fundus photography (including stereo photographs for fields 1, 2, and 3)
- AE and serious adverse event (SAE) monitoring
- Concomitant medication, procedures, and treatment review

Subjects who meet all of the inclusion criteria and none of the exclusion criteria will be assigned a subject number and will be enrolled into the study. The Investigator will assign the order in which the eyes are treated (i.e., SE1 and SE2, respectively). This will be done in collaboration with the subject; however, the worse eye will generally be selected for treatment first. Study eye selection and eligibility for surgery will then be confirmed collectively by the Patient Eligibility Review Committee, which includes the Investigator, a consulting surgeon, and the Sponsor (see the Patient Eligibility Review Plan). The target interval between the surgical procedures of SE1 and SE2 will be determined at this visit.

For each subject, the interval between SE1 and SE2 treatment is expected to range from weeks to months. While this interval will be decided on a case-by-case basis, an effort will

be made to schedule varying treatment intervals in order to better characterise the immunological and safety profile of sequential treatment administration and to reflect the anticipated real-world application of the study drug. Thus, approximately 20 subjects will be treated with a short- (<6 month), medium- (6-12 months), or long- (>12 month) duration surgery window between treatment of the first and second eye. Because the timing of the second surgery visit (Period 2, Visit 1) will vary among subjects, the duration of study Period 1 will also be variable. To avoid unnecessary study visits, every effort should be made by the Investigator to schedule Period 2, Visit 1 to coincide with a planned Period 1 post-treatment visit.

The next study visit (i.e., surgery and dosing, Period 1, Visit 1) is to be scheduled within 10 weeks of the Screening Period. Subjects will attend Period 1, Visits 2-9 unless the second surgery visit (Period 2, Visit 1) begins, which will mark the start of study Period 2. Because the timing of the second surgery visit (Period 2, Visit 1) will vary among subjects, the duration of study Period 1 will also be variable.

Subjects will be treated with oral corticosteroids (e.g., prednisolone / prednisone) during the peri-operative period for each eye. They will be instructed to start taking the drug 2 days before their surgery at Period 1, Visit 1 for SE1. For SE1, the Full Corticosteroid Regimen should be initiated, as described in [Section 9.8](#).

For SE2 surgeries that occur on Day 21 or later, the Full Corticosteroid Regimen should be initiated as described, beginning 2 days before the scheduled surgery.

If SE2 is to be performed prior to Study Day 21, then the Full Corticosteroid Regimen should be initiated 2 days prior to the scheduled surgery for SE2, and this will supersede the steroid taper in progress for SE1. The full 21 days of treatment will then be completed for SE2.

Subjects will be issued a diary card to capture corticosteroid compliance. Subjects will also be instructed to use barrier contraception or abstain from sexual intercourse for a period of 3 months from the time they are treated.

The schedule of procedures is identical for Periods 1 and 2; during each period, procedures are to be conducted in both SE1 and SE2.

If a subject has previously participated in a clinical trial of AAV2-REP1 for the treatment of CHM and has received AAV2-REP1 in one eye, the untreated eye will be assigned as SE2 at the Screening Visit and the subject will immediately enter Period 2.

10.1.1 Baseline Visit, Period 2 (<10 Weeks from Visit 1, Period 2 [SE2])

The following baseline assessments for Period 2 must be performed within 10 weeks prior to surgery for SE2 (Visit 1, Period 2). If the assessments have not been performed within a regularly scheduled visit within this window, an additional visit is required.

- Vital signs
- Weight
- Vector shedding sampling – blood, tears (both eyes), urine, saliva
- Immunogenicity sampling
- BCVA
- Microperimetry

- Full ophthalmic examination, including IOP, a slit-lamp examination, lens opacity, and dilated fundus examination
- SD-OCT
- AF
- 7-field colour fundus photography (including stereo photographs for fields 1, 2, and 3)
- AE and SAE monitoring
- Concomitant medication, procedures and treatment review

Eligibility for SE2 surgery will then be confirmed collectively by the Patient Eligibility Review Committee, which includes the Investigator, a consulting surgeon, and the Sponsor (see the Patient Eligibility Review Plan).

If BCVA in SE2 is <34 ETDRS letters, surgery may be performed when, in the opinion of the Patient Eligibility Review Committee:

1. the subject is found eligible by all other inclusion and exclusion criteria, and
2. the subject is considered an appropriate candidate who has potentially modifiable disease.

10.2 Period 1 and 2, Visit 1 (Day 0, Injection Day Visit)

At Visit 1 (Day 0, Injection Day Visit), the following assessments will be performed:

- Full ophthalmic examination, including IOP, a slit-lamp examination, lens opacity, and dilated fundus examination
- AE/SAE monitoring
- Concomitant medication, procedures, and treatment review (including review of the corticosteroid diary card)

It may be necessary for subjects to undergo a pre-surgical workup according to local hospital procedures (e.g., blood draw for anesthetist) which are outside of the protocol-defined assessments. Any assessments performed outside of the protocol will not be collected as part of the study analysis.

Subjects will then undergo vitrectomy and receive a volume of up to 0.1 mL sub-retinal injection of AAV2-REP1, containing 1×10^{11} gp (see [Section 9.4](#) for details). Subjects will be carefully monitored for the occurrence of AEs during the procedure. Subjects will return to the site 1, 3, 7 and 14 days after surgery for post-operative follow-up (Visit 2 [Day 1], Visit 3 [Day 3 + 2 Days], Visit 4 [Day 7 -1/+2 Days] and Visit 5 [Day 14 ± 3 Days], respectively).

The post-operative outcome and visual function of SE1 will inform the scheduling of Period 2. Significant signs of post-operative inflammation or other post-operative sequelae, as judged by the Investigator, should be resolved in SE1 for the subject to continue to Period 2. After a comprehensive evaluation of all safety assessments and visual functional tests of SE1 and SE2, the Investigator will decide the appropriate time to schedule SE2, Visit 1. If severe ocular inflammation or any other post-operative sequela that is unresponsive to treatment occurs in SE1, the second eye should not be treated. However, Period 1 should be continued for monitoring of safety for the duration of the study.

To allow accurate characterisation of AAV2-REP1 safety and immunogenicity profile, treatment of SE2 should not occur if a previous intraocular surgery was performed on the same eye within 3 months of the planned treatment date. If intraocular surgery has occurred within 3 months, treatment of SE2 should be delayed until such a time that the 3-month interval has elapsed and there is complete post-operative recovery of the eye.

10.3 Period 1 and 2, Visit 2 (Post-operative Day 1)

For Visit 2, ocular assessments and procedures will be performed on each eye. At Visit 2 (Post-operative Day 1), subjects will return to the site for their first post-operative visit for the same eye that underwent surgery at Visit 1 (Period 1 [SE1] or Period 2 [SE2]). The following assessments will be performed:

- Vital signs
- Vector shedding sampling – blood, tears (both eyes), urine, saliva
- Immunogenicity sampling
- BCVA
- Full ophthalmic examination, including IOP, a slit-lamp examination, lens opacity, and dilated fundus examination
- SD-OCT
- AE/SAE monitoring
- Concomitant medication, procedures, and treatment review (including review of the corticosteroid diary card)

10.4 Period 1 and 2, Visit 3 (Post-operative Day 3 + 2 Days)

For Visit 3 (Post-operative Day 3 + 2 Days), ocular assessments and procedures will be performed on each eye. At Visit 3 (Day 3+ 2 Days), subjects will return to the site for their second post-operative visit for the same eye that underwent surgery at Visit 1 (Period 1 [SE1] or Period 2 [SE2]). The following assessments will be performed:

- Vital signs
- Vector shedding sampling – blood, tears (both eyes), urine, saliva
- BCVA
- Full ophthalmic examination, including IOP, a slit-lamp examination, lens opacity, and dilated fundus examination
- AE/SAE monitoring
- Concomitant medication, procedures and treatment review (including review of the corticosteroid diary card)

10.5 Period 1 and 2, Visit 4 (Post-operative Day 7 -1/+2 Days)

For Visit 4 (Post-operative Day 7 -1/+2 days), ocular assessments and procedures will be performed on each eye. At Visit 4 (Day 7 -1/+2 days), subjects will return to the site for their third post-operative visit for the same eye that underwent surgery at Visit 1 (Period 1 [SE1] or Period 2 [SE2]). The following assessments will be performed:

- Vector shedding sampling – blood, tears (both eyes), urine, saliva

- Immunogenicity sampling
- BCVA
- Full ophthalmic examination, including IOP, a slit-lamp examination, lens opacity, and dilated fundus examination
- SD-OCT
- AF
- AE/SAE monitoring
- Concomitant medication, procedures and treatment review (including review of the corticosteroid diary card)

10.6 Period 1 and 2, Visit 5 (Post-operative Day 14 ± 3)

For Visit 5 (Post-operative Day 14 ± 3 days), ocular assessments and procedures will be performed on each eye. At Visit 5 (Day 14 ± 3 days), subjects will return to the site for their fourth post-operative visit for the same eye that underwent surgery at Visit 1 (Period 1 [SE1] or Period 2 [SE2]). The following assessments will be performed:

- Vector shedding sampling – blood, tears (both eyes), urine, saliva
- Immunogenicity sampling
- BCVA
- Full ophthalmic examination, including IOP, a slit-lamp examination, lens opacity, and dilated fundus examination
- SD-OCT
- AF
- AE/SAE monitoring
- Concomitant medication, procedures and treatment review (including review of the corticosteroid diary card)

10.7 Period 1 and 2, Visit 6 (Month 1 ± 7 Days) and Visit 7 (Month 3 ± 14 Days)

For Visit 6 (Month 1 ± 7 days) and Visit 7 (Month 3 ± 14 days), ocular assessments and procedures will be performed on each eye. The following assessments will be performed:

- Vector shedding sampling – blood, tears (both eyes), urine, saliva
- Immunogenicity sampling
- BCVA
- Full ophthalmic examination, including IOP, a slit-lamp examination, lens opacity, and dilated fundus examination
- SD-OCT
- AF
- Microperimetry
- AE/SAE monitoring

- Concomitant medication, procedures and treatment review (including review/return of the corticosteroid diary card at Visit 6)

10.8 Period 1 and 2, Visit 8 (Month 6 ± 14 Days) and Visit 9 (Month 12 ± 14 Days)*

For Visit 8 (Month 6 ± 14 days) and Visit 9 (Month 12 ± 14 days), ocular assessments and procedures will be performed on each eye. The following assessments will be performed:

- Vital signs (Visit 9, Month 12 only)
- Immunogenicity sampling
- BCVA
- Full ophthalmic examination, including IOP, a slit-lamp examination, lens opacity, and dilated fundus examination
- SD-OCT
- AF
- Microperimetry
- 7-field colour fundus photography (including stereo photographs for fields 1, 2, and 3) (Visit 9, Month 12 only)
- AE/SAE monitoring
- Concomitant medication, procedures and treatment review

10.9 Early Termination (ET Visit)

In the event that a subject discontinues the study at any time, the site should use every reasonable effort to ensure that an ET Visit is conducted. The following assessments should be performed (all ophthalmic assessments will be conducted on both eyes):

- Vital signs
- Vector shedding sampling – blood, tears (both eyes), urine, saliva (only if the ET Visit occurs within 3 months post-treatment)
- Immunogenicity sampling
- BCVA
- Full ophthalmic examination, including IOP, a slit-lamp examination, lens opacity, and dilated fundus examination
- SD-OCT
- AF
- Microperimetry
- 7-field colour fundus photography (including stereo photographs for fields 1, 2, and 3)
- AE/SAE monitoring
- Concomitant medication, procedures and treatment review (including review/ return of the corticosteroid diary card, if applicable)

10.10 Unscheduled Visits

If clinically indicated, subjects may need to return to the site for an unscheduled visit. At a minimum, the following assessments will be performed (ophthalmic assessments will be conducted on any eye deemed appropriate by the Investigator):

- BCVA
- Full ophthalmic examination, including IOP, a slit-lamp examination, lens opacity, and dilated fundus examination
- SD-OCT
- AE/SAE monitoring
- Concomitant medication, procedures and treatment review (including review / return of the corticosteroid diary card, if applicable)

11 ASSESSMENT OF SAFETY

11.1 Evaluation, Recording, and Reporting Adverse Events

11.1.1 Definitions

11.1.1.1 Adverse Event

An AE is any untoward medical occurrence in a clinical investigation subject, which does not necessarily have a causal relationship with the study drug/surgical procedure. An AE can therefore be any unfavourable and unintended sign (including an abnormal laboratory finding), symptom, or disease temporally associated with the use of the study drug/surgical procedure, whether or not related to the investigational product or with the surgical procedure described in this protocol.

AEs are to also include any pre-existing condition (other than CHM) or illness that worsens during the study (i.e., increases in frequency or intensity).

Worsening of the signs, symptoms and visual function related to CHM is not to be considered an AE unless, in the opinion of the Investigator, the changes are not consistent with the natural progression of the disease.

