1997, Cheng, Azen et al. 2001, Anderson, Fineman et al. 2006, Stein, Zacks et al. 2009, Recchia, Scott et al. 2010). Post-operative intraocular inflammation caused by vitrectomy is often associated with transient or sometimes permanent visual impairment. Another complication of vitrectomy is cataract formation, which may require an additional surgical procedure (cataract extraction) (Park, Marcus et al. 1995, Cheng, Azen et al. 2001, Recchia, Scott et al. 2010). In addition, the surgical procedure is performed under general anesthesia, which includes the risks of dizziness, confusion, nausea and vomiting.

Loss of VA has been observed post-treatment with AAV2-REP1. This VA loss was determined by the Investigators to be plausibly related to the administration of AAV2-REP1, however without definitively attributing the cause to either the study procedure or the GTMP. Complications from the surgical procedure are expected and are not considered reportable as suspected unexpected serious adverse reactions (SUSARs) unless also assessed to be at least possibly related to AAV2-REP1. The Reference Safety Information described in the current version of the Investigator's Brochure for AAV2-REP1 defines *visual acuity reduced* as an expected serious adverse drug reaction, with a frequency of 4/79 (5.1%), defined as common ($\geq 1/100$ to $<1/10$). Loss of VA is considered an identified risk of AAV2-REP1. Inflammation is a potential risk of AAV2-REP1.

See the Investigator's Brochure for further details.

Thus, although there are risks associated with the administration of the study treatment via vitrectomy and retinal detachment, the potential for benefit in the form of improved VA that may be provided to subjects with CHM following treatment with AAV2-REP1 provides an acceptable risk-benefit profile for participation in this study.

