11.1.1.2 Serious Adverse Event

An SAE is defined as any untoward medical occurrence that:

- Results in death
- Is life-threatening
- Requires inpatient hospitalisation or prolongation of existing hospitalisation
- Results in persistent or significant disability/incapacity
- Is a congenital anomaly/birth defect
- Results in vision loss or is vision threatening
- Is another important medical event(s)

The term 'life-threatening' in the definition of 'serious' refers to an event in which the subject is at risk of death at the time of the event. It does not refer to an event that hypothetically might cause death if it were more severe.

Hospitalisation that was pre-scheduled prior to obtaining the consent to participate in the study or for an elective procedure or routinely scheduled treatment for a pre-existing condition which has not worsened, does not constitute an SAE.

A prescheduled or elective procedure or a routinely scheduled treatment will not be considered an SAE, even if the subject is hospitalized. The study site must document all of the following:

- The prescheduled or elective procedure or routinely scheduled treatment was scheduled (or was on a waiting list to be scheduled) prior to obtaining the subject's consent to participate in the study.
- The condition requiring the prescheduled or elective procedure or routinely scheduled treatment was present before and did not worsen or progress in the opinion of the Investigator between the subject's consent to participate in the study and the time of the procedure or treatment.

- The prescheduled or elective procedure or routinely scheduled treatment is the sole reason for the intervention or hospital admission.

If a subject is hospitalized due to local requirements for administration of the study treatment, the hospitalization should not be considered an SAE unless one of the requirements in [Section 11.1.1.2](#) is met.

Other events that may not result in death, are not life-threatening or do not require hospitalisation, may be considered an SAE when, based upon appropriate medical judgment, the event may jeopardise the subject and may require medical or surgical intervention to prevent 1 of the outcomes listed above.

Vision Loss to be Reported as Serious Adverse Events

Vision Loss not to be Reported as an SAE:

- Surgery-related BCVA decrease of ≥ 15 letters on ETDRS chart occurring within 1 day of surgery, but recovering / resolving at post-operative Days 7 and 14.

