Vision Loss or Vision-Threatening Event to be Reported as an SAE:

- Surgery-related BCVA decrease of ≥ 15 letters on ETDRS chart that occurs within 1 day of surgery and that has not recovered* by the 1-Month Visit.
- A decrease in BCVA of ≥ 15 letters on ETDRS chart that occurs within 1 day of surgery, however, in the Investigator's opinion:
 - Has an evolution not consistent with the expected post-operative course;
 - May be attributable to a complication that occurred during surgery, or another untoward event, or the study drug;
 - Actually or potentially requires any surgical or medical intervention to prevent permanent loss of vision.
- Non-surgery-related, sustained (>48 hours duration) decrease from baseline in BCVA of ≥ 15 letters on ETDRS chart.

*Recovery / Resolution of BCVA is defined as a return to baseline BCVA within 5 letters on the ETDRS chart.

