Both counts of subjects and events will be reported. A subject with more than one occurrence of the same AE in a particular SOC will be counted only once in the total of those experiencing AEs in that particular SOC.

If a subject experiences the same AE at more than one severity, the most severe rating will be given precedence.

If a subject experiences the same AE at more than one relationship to study drug/procedure, causal relationship will be given precedence over no causal relationship. However, where a causal relationship is identified by the Investigator, the subject will be counted once within each sub-category (Study Drug, Study Procedure, Study Drug and Study Procedure, unknown).

In the summary tables, related events are defined as events that are assessed by the investigator to be related to study drug/procedure/both or with an unknown relationship.

AEs will be assigned to Period 1 or Period 2 based on the AE Start Date. An AE with a start date on or after the day of surgery of Study Eye 2 will be attributed to Period 2; otherwise, the AE will be attributed to Period 1.

An ocular event is an event where the site of the event is reported as OU, OD or OS. Where an event is recorded as 'OU', it will be counted once for each eye (SE1 and SE2).

Separate additional summaries will be provided for adverse events classified as Ocular Inflammation and Visual Acuity Reduced. The lists of PTs assigned to Ocular Inflammation and Visual Acuity Reduced are provided in a separate document (BIIB111 Signal Detection Plan). The following summaries will be provided by eye, by period (or by surgery window), and overall:

- Ocular Inflammation-related TEAEs by SOC and PT
- Ocular Inflammation-related TEAEs by SOC and PT, and by time to onset (≤ 30 days; > 30 days)
- Visual Acuity Reduced-related TEAEs by SOC and PT
- Visual Acuity Reduced-related TEAEs by SOC and PT, and by time to onset (≤ 30 days; > 30 days)

Imputation rules for partial dates are presented in Appendix 7.1.

The following listings will be provided:

- All AEs
- AEs leading to death

AEs will be coded according the MedDRA version 23.0 or higher.

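### Protocol 11.1.1.1 and 11.1.1.2 conflict on a sustained, non-surgical loss of 15 or more letters that the investigator attributes to choroideremia: one makes it no AE, the other an SAE, and neither is said to govern

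*Protocol*

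**What the plan says.** Protocol 11.1.1.1 defines an AE without requiring a causal link to treatment, then makes an exception for the disease under study: "Worsening of the signs, symptoms and visual function related to CHM is not to be considered an AE unless, in the opinion of the Investigator". Such worsening counts as an AE only if the investigator judges that "the changes are not consistent with the natural progression of the disease". The exception has no letter threshold and does not mention 11.1.1.2.

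Protocol 11.1.1.2 opens with "An SAE is defined as any untoward medical occurrence that" meets one of a list of criteria, among them "Results in vision loss or is vision threatening". Its vision-loss rules then list as reportable: "Non-surgery-related, sustained (>48 hours duration) decrease from baseline in BCVA of ≥ 15 letters on ETDRS chart". That item carries no exception for disease progression and does not mention 11.1.1.1.

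Protocol 5.4 says of this outcome: "Loss of VA is considered an identified risk of AAV2-REP1". Protocol 9.6 provides no masking, and the synopsis lists no comparator.

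On the analysis side, SAP 4.17.10 says "Separate additional summaries will be provided for adverse events classified as Ocular Inflammation and Visual Acuity Reduced", built from reported events. SAP 4.17.1 separately counts eyes losing at least 5, 10 and 15 letters from measured BCVA. SAP 4.17.11.4 sets a measured count of eyes losing 15 or more letters at Month 12 beside its AE rows.

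**The concern.** Safety is the sole objective of this study, and loss of visual acuity is the risk already identified for the product. Whether a large, late loss enters the safety database should not depend on which of two adjacent sections a site reads first.

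As written, it can. A loss handled under 11.1.1.1 gets no AE form and no 24-hour report under 11.1.4. It is then absent from the TEAE and serious TEAE tables, the Visual Acuity Reduced summaries and the AE rows of the immunogenicity-safety analysis. The same loss handled under 11.1.1.2 appears in all of them. The choice rests with an investigator who knows the eye was treated, in a trial with no control arm. The AE tables and the measured BCVA tables could then disagree, and the plan has no rule or listing to explain the difference.

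**Working it through.** This is mainly a comparison of text.

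**1. One case, two routes.** Take a treated eye down 16 letters at Month 12, with no surgical cause, the loss confirmed beyond 48 hours, and the investigator attributing it to choroideremia.

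| Step | Under 11.1.1.1 | Under 11.1.1.2 |
|---|---|---|
| Deciding factor | Investigator's view of natural progression | Size (16 ≥ 15), duration, not surgical |
| Letter threshold | None | 15 |
| Exemption for disease | Yes | None |
| Classification | Not an AE | SAE |
| 24-hour report (11.1.4) | No | Yes |
| In TEAE, serious TEAE and Visual Acuity Reduced tables | No | Yes, once coded to a listed term |
| In measured BCVA loss tables | Yes | Yes |

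**2. Does one rule supersede the other?** The Version 3.0 summary of changes shows both wordings entering in that same amendment, so neither replaced the other. No precedence is stated.

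**3. Does the structure imply precedence?** The evidence points both ways. In 11.1.1.2 one of the items on loss within a day of surgery turns expressly on the investigator's opinion, while the non-surgical item does not, which suggests a deliberate hard rule. But 11.1.2 records seriousness as an attribute of each AE, so a site that stops at 11.1.1.1 has no AE to mark as serious.

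**4. Which baseline?** The 11.1.1.2 item measures from baseline without saying which. SAP 4.3 resets the SE1 baseline at Period 2. If SE1 is down 16 letters from its Period 1 baseline and 2 of those went before the second surgery, the loss against the Period 2 baseline is 16 − 2 = 14, below the threshold of 15.

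**5. Can a size be derived?** The only relevant figure is the reference frequency in Section 5.4: 4/79 = 0.0506, which reproduces the stated 5.1% and lies in the 1/100 to 1/10 band. The Clopper-Pearson 95% interval is 1.4% to 12.5%. This is a frequency of serious adverse drug reactions. Losses judged to be progression are a different category, and their frequency appears nowhere.

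**6. What one judgement is worth.** SAP 4.17.10 bases AE percentages on subjects. With the planned numbers, one subject reclassified (with no other such event) moves the overall figure by 1/60 = 1.67 percentage points, and the figure for a surgery window of about 20 subjects by 1/20 = 5 points. This is the unit of change. It does not estimate how many cases will arise.

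**The case against.** The strongest reply is that a specific, quantified rule headed as reportable naturally overrides a general exemption. A site reading it that way would report every such loss, and nothing would be missed. That reading is reasonable, but the protocol does not state it, and 11.1.2 leaves room for the other one. If it is the intended reading, writing it down costs one sentence. The same reply does defeat a stronger inference, that these losses never reach the AE database. What the documents support is possible inconsistency between sites.

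A second reply is that measured BCVA is itself a listed safety measure, tabulated without passing through the AE definition. This stands, and it rules out the inference that every count of the identified risk depends on opinion. The measured tables are not a full substitute: they trigger no expedited report, they do not apply the 48-hour condition, and the by-period tables use the reset SE1 baseline (a supportive analysis in SAP 4.16.1 keeps the Period 1 baseline).

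A reader might also infer from Section 5.4 that natural progression cannot be checked within the trial. The text does not say so: the uncertainty it describes is between procedure and product, not between treatment and disease. Both eyes are assessed in Period 1 while SE2 is untreated, images go to a central reading centre, and a DMC reviews accruing data. These give an imperfect check, although none is assigned to decide whether a loss is an AE.

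Finally, a reader might take 120 × 4/79 = 6.08 expected events, remove 1 to 3 as progression, and report a fall to 5.08/120 = 4.2% or 3.08/120 = 2.6%. That subtraction is invalid, because the four reference cases were already counted as reactions to treatment. The number removed would be invented. The base of 120 also overlooks the 6 subjects whose first eye was treated in an earlier study (120 − 6 = 114 eyes treated here, if 60 subjects all complete both surgeries).

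**Conclusion.** The conflict is real and can be read directly from the text: the same loss is an SAE under one section and not an AE under the other, with no stated precedence. Its reach is limited to AE, SAE and Visual Acuity Reduced TEAE counts, the AE rows of SAP 4.17.11.4, and expedited reporting. The measured letter-loss counts in SAP 4.17.1 and the Month 12 count in 4.17.11.4 do not change.

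No overall magnitude can be given, since the documents do not say how often choroideremia alone produces a sustained loss of this size within the follow-up, or how sites would classify it. The conclusion assumes only that at least one such loss occurs and is attributed to the disease. The point should be corrected, because safety is the primary objective and the remedy is small. The measured tables keep it from being more serious than that.

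**What to change.** Add to Protocol 11.1.1.1: *This exemption does not apply to BCVA losses that meet the vision-loss SAE criteria in Section 11.1.1.2; these are reported under that section, and presumed natural progression is recorded in the causality assessment.*

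Leave the scope of 11.1.1.2 as it is: either eye, non-surgery-related for this item, and with its existing exclusion for surgery-related loss that is resolving. Limiting the new sentence to treated eyes would leave the same conflict for an untreated SE2 in Period 1. State in 11.1.1.2 which baseline applies to SE1 during Period 2.

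Add to the SAP a listing of every eye with a measured loss of 15 or more letters, matched to its AE/SAE record or marked as having none. It uses data already collected, so it is worth having even if the protocol can no longer be amended.

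The cost is one sentence plus a baseline definition, matching guidance to sites, and one listing. The downside is that some losses due to the disease will be reported as SAEs, with the presumed cause on record.
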